Study Title: Improving Influenza Vaccination Delivery Across a Health System by the Electronic Health Records Patient Portal RCT 5

Initial IRB Approval: 12/20/2017

RCT 5 IRB Approval: 8/18/2022

Clinical Trials Registration: NCT05525494

Protocol

Brief Summary:

This trial is taking place in Los Angeles, CA among patients from primary care practices within the UCLA Health System.

Despite the Advisory Committee on Immunization Practices (ACIP) recommendation in 2010 that all people above 6 months of age should receive an annual flu vaccine, vaccination rates remain low. The investigators plan to assess the effectiveness of text and portal reminder/recall messages with direct appointment scheduling (pre-appointment, and no pre-appointment) encouraging influenza vaccinations sent to patient portal users, as well as the effectiveness of tailored portal reminder/recall messages based on responses from pre-commitment prompt asking which time and which place they plan to receive their influenza vaccine using a 2 x 2 nested factorial design.

Methods and Procedures

We propose a three-arm randomized controlled trial, and a 2 x 2 nested factorial design within the intervention arms. Patients are randomized within UCLA primary care practices into 1) receiving text based R/R messages with direct scheduling link, 2) portal-based R/R messages with direct scheduling link, or 3) the control group. Patients randomized to the intervention arms will receive reminders if they are due for influenza vaccine.

Nested within the portal reminder arm, we will have two additional components for which patients will be randomized separately: 1) A pre-commitment prompt, asking patients which time (September, October, November or December) and which place (UCLA, pharmacy, workplace or school, or other) they plan to get their Influenza vaccine with tailored monthly messages based on responses (pre-commitment message with tailored recall messages with direct scheduling vs. standard (“fixed”) portal reminders with direct scheduling); 2) A pre-appointment reminder encouraging patients to ask for their influenza vaccine at their upcoming appointment (pre-appointment reminder encouraging influenza vaccination vs. standard pre-appointment reminder not mentioning influenza vaccination)

Nested within the text message reminder arm, we will have one additional component for which patients will be randomized separately: 1) A pre-appointment reminder encouraging patients to ask for their influenza vaccine at their upcoming appointment (pre-appointment reminder encouraging influenza vaccination vs. standard pre-appointment reminder not mentioning influenza vaccination).

Spacing of R/R messages: The pre-commitment prompt will be sent in September, direct appointment scheduling and no direct appointment scheduling reminders will be sent one time per month until record of vaccine receipt appears in the patient EHR in October, November, and December. The pre-appointment reminders will be sent 2-4 days in advance of scheduled visits.

Languages: messages will be in English.

Health Literacy: We will use plain language <7th grade reading level per Flesch-Kincaid analysis.

Eligibility: Our EHR will identify subjects who are eligible for either 1 or 2 influenza vaccinations based on ACIP algorithms (2 are recommended for children <9 years who have not had prior vaccination).

Inclusion criteria

Inclusion criteria will involve-- all UCLA primary care patients over 4 months of age who have made at least 1 visit to the practice within the prior 3 years and who have signed up for MyUCLAhealth (UCLA's portal) and have used the portal at least once within 12 months, from these patients, index patients per household will be randomly selected.

- a. Active patient: We selected >1 visit in 3y based on our prior studies and the literature to focus the intervention on active patients; practices do not have a good mechanism to inactivate patients.
- b. Focusing on Portal Users: We can only send portal R/R messages to patients who have signed up for the portal. Since some patients sign up for the portal but never use it we will restrict our inclusion criteria to patients who used the portal within 12m (75% of UCLA patients). This standard has been applied before. We will assess intervention effects for the included population, and also for the entire practice, since the impact of the intervention reflects the extent of portal penetration.

Exclusion criteria

Patients will be excluded if they are not a patient at one of the 67 primary care practices within UCLA's Health System, and/or if they do not meet the above specified requirements for being an active patient or portal user.

Main Outcomes and Measures

Primary Measures:

- 1) Receipt of >1 influenza vaccine among index patients between 9/1/2022-4/1/2023 as documented in the EHR which is supplemented electronically by the health system with influenza vaccination data from external sources (e.g., pharmacies) and claims data.
- 2) Receipt of >1 influenza vaccine among pediatric index patients between 9/1/2022-4/1/2023 as documented in the EHR which is supplemented electronically by the health system with influenza vaccination data from external sources (e.g., pharmacies) and claims data.

Secondary Measures: Receipt of annual influenza vaccine between 9/1/2022-4/1/2023 among all included patients in identified households.

Study Arm	Intervention/Treatment

Active Comparator: Text Fixed R/R Messages with Direct Appointment Schedule Link + Text Pre-Appointment Reminders
 
Participants in this arm will receive up to 3 R/R messages by text. R/R message will be sent with a Direct Appointment Scheduling link and instructions to make a flu vaccine appointment. Participants will receive a Pre-Appointment Reminder via text when they schedule a visit during the study period.
	
Behavioral: Text Fixed R/R Messages with Direct Appointment Schedule Link
 
Participants in this arm will receive up to 3 R/R messages by text. R/R message will be sent with a Direct Appointment Scheduling link and instructions to make a flu vaccine appointment.
 
Behavioral: Text Pre-Appointment Reminder
 
Participants will receive a Pre-Appointment Reminder via text when they schedule a visit during the study period.

Active Comparator: Text Fixed R/R Messages with Direct Appointment Schedule Link
 
Participants in this arm will receive up to 3 R/R messages by text. R/R message will be sent with a Direct Appointment Scheduling link and instructions to make a flu vaccine appointment.
	
Behavioral: Text Fixed R/R Messages with Direct Appointment Schedule Link
 
Participants in this arm will receive up to 3 R/R messages by text. R/R message will be sent with a Direct Appointment Scheduling link and instructions to make a flu vaccine appointment.


Active Comparator: Portal Pre-Commitment Prompt, Tailored R/R Messages w/ Direct Scheduling + Pre-Appointment Reminders
 
Participants in this arm will receive a pre-commitment prompt message by portal in September. Tailored R/R messages will be sent monthly by portal based on time and place selected by patients (up to 3). R/R message will be sent with a Direct Appointment Scheduling link and instructions to make a flu vaccine appointment.
 
Participants will receive a Pre-Appointment Reminder advising them to ask their doctor for the flu vaccine at their upcoming appointment via portal when they schedule a visit during the study period.
	
Behavioral: Portal Pre-Commitment Prompt with Tailored R/R Messages with Direct Appointment Schedule Link
 
Participants in this arm will receive a pre-commitment prompt message by portal in September. Tailored R/R messages will be sent monthly by portal based on time and place selected by patients (up to 3). R/R message will be sent with a Direct Appointment Scheduling link and instructions to make a flu vaccine appointment.
 
Behavioral: Portal Pre-Appointment Reminder
 
Participants will receive a Pre-Appointment Reminder advising them to ask their doctor for the flu vaccine at their upcoming appointment

	via portal when they schedule a visit during the study period.
Active Comparator: Portal Pre-Commitment Prompt with Tailored R/R Messages with Direct Appointment Schedule Link Participants in this arm will receive a pre-commitment prompt message by portal in September. Tailored R/R messages will be sent monthly based on time and place selected by patients (up to 3). R/R message will be sent with a Direct Appointment Scheduling link and instructions to make a flu vaccine appointment.	Behavioral: Portal Pre-Commitment Prompt with Tailored R/R Messages with Direct Appointment Schedule Link Participants in this arm will receive a pre-commitment prompt message by portal in September. Tailored R/R messages will be sent monthly by portal based on time and place selected by patients (up to 3). R/R message will be sent with a Direct Appointment Scheduling link and instructions to make a flu vaccine appointment.
Active Comparator: Portal Fixed R/R Messages with Direct Appointment Schedule Link + Portal Pre-Appointment Reminder Participants in this arm will receive up to 3 R/R messages by portal. R/R message will be sent with a Direct Appointment Scheduling link and instructions to make a flu vaccine appointment. Participants will receive a Pre-Appointment Reminder advising them to ask their doctor for the flu vaccine at their upcoming appointment via portal when they schedule a visit during the study period.	Behavioral: Portal Fixed R/R Messages with Direct Appointment Schedule Link Participants in this arm will receive up to 3 R/R messages by portal. R/R message will be sent with a Direct Appointment Scheduling link and instructions to make a flu vaccine appointment. Behavioral: Portal Pre-Appointment Reminder Participants will receive a Pre-Appointment Reminder advising them to ask their doctor for the flu vaccine at their upcoming appointment via portal when they schedule a visit during the study period.
Active Comparator: Portal Fixed R/R Messages with Direct Appointment Schedule Link Participants in this arm will receive up to 3 R/R messages by portal. R/R message will be sent with a Direct Appointment Scheduling link and instructions to make a flu vaccine appointment.	Behavioral: Portal Fixed R/R Messages with Direct Appointment Schedule Link Participants in this arm will receive up to 3 R/R messages by portal. R/R message will be sent with a Direct Appointment Scheduling link and instructions to make a flu vaccine appointment.
No Intervention: No R/R Message or Pre-Appointment Reminder	

Participants do not receive any flu vaccine R/R message or Pre-Appointment Reminder advising them to ask their doctor for the flu vaccine at their upcoming appointment during the specified flu season.

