Study Title: Improving Influenza Vaccination Delivery Across a Health System by the Electronic Health Records Patient Portal RCT 5

Initial IRB Approval: 12/20/2017

RCT 5 IRB Approval: 8/18/2022

Clinical Trials Registration: NCT05525494

Statistical Analysis

Primary Analysis

We hypothesize that patients receiving text R/R messages will have higher influenza vaccination rates than portal R/R messages and no R/R; we hypothesize patients receiving the pre-commitment prompt will have higher influenza vaccination rates than standard portal R/R messages and no R/R; and we hypothesize that patients receiving pre-commitment prompts will have higher influenza vaccination rates than no prompts. Primary outcomes (patient receipt of flu vaccine) are binary; our main explanatory variable will be an indicator for the receipt of any portal-based R/R or prompt.

The primary outcome will be the patient's end of flu season vaccination status. Intervention effects will be assessed using mixed effects log-binomial models. Models will contain terms for messaging modality (text v. portal v. none), pre-appointment reminders (sent v. not sent), and, for the portal intervention arm, a pre-commitment prompt (sent v. not sent; this is not included in the text-based arm). Models will adjust for patient characteristics, including age, sex, race/ethnicity, primary language, primary insurer, and prior year vaccination status. Practice random effects will be used to account for clustering of patients by primary care practice. Primary assessment will involve performing model contrasts, and a significance level of 0.017 will be used (3-fold Bonferroni correction of 0.05). To evaluate the combined effect of interventions, we will fit a second model introducing interactions between messaging modality and the other two intervention terms. These analyses will use a significance level of 0.05. Intervention effects will be summarized in terms of risk ratios and 95% confidence intervals.

For RCT #5, individual patients who opt out of text messages will be excluded from the final analysis. In addition, if practices do not send pre-appointment reminders via text, for the pre-appointment analysis the patients from the practice will be excluded from the final analysis. In addition, non-portal users will be excluded from the final analyses.

Secondary Analysis

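### The primary outcome counts doses from 9/1/2022, but text and fixed-portal messages start in October and patients already vaccinated stay in, so these two comparisons with control are diluted

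*Protocol*

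**What the plan says.** **Outcome.** Protocol, Main Outcomes and Measures, first primary measure: "Receipt of >1 influenza vaccine among index patients between 9/1/2022-4/1/2023 as documented in the EHR". I read >1 as at least one, because the Protocol uses the same symbol for its visit criterion, which it also words as at least 1 visit. The pediatric primary measure and the household secondary measure use the same dates. SAP, Primary Analysis: "The primary outcome will be the patient's end of flu season vaccination status", with no dates.

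**Message timing.** Protocol, Spacing of R/R messages: "The pre-commitment prompt will be sent in September". The monthly reminders follow "in October, November, and December". Pre-appointment reminders go out 2-4 days before a visit, with no start date.

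**Who enters.** Inclusion covers "all UCLA primary care patients over 4 months of age who have made at least 1 visit to the practice within the prior 3 years", plus portal use within 12 months and random selection of one index patient per household. Exclusion covers patients outside the 67 practices and applies "if they do not meet the above specified requirements for being an active patient or portal user". Neither list mentions a dose already received this season.

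**What being due does.** Protocol, Methods and Procedures: "Patients randomized to the intervention arms will receive reminders if they are due for influenza vaccine". It decides who is messaged after allocation.

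**SAP exclusions and covariates.** The SAP removes patients who opt out of texts, patients of practices that send no text pre-appointment reminders (for that analysis) and non-portal users. It adjusts for prior-year vaccination, not for a current-season dose before the first message. Neither document gives a randomisation date.

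**The concern.** The outcome clock starts on a calendar date and the R/R intervention starts at least a month later. A patient vaccinated in September is no longer due, so normally gets no October message, yet scores as a success in whichever arm he or she was allocated to. That patient's outcome was settled before text or fixed-portal R/R began and says nothing about its effect.

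There is a reverse case. A patient with a season dose dated before 9/1 is also no longer due and is not messaged (a child who needs two doses may be an exception), but counts as unvaccinated under the Protocol's window.

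At stake are the size of the risk ratio for text and fixed-portal R/R against control, and the power of contrasts tested at 0.017.

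**Working it through.** The documents give no sample size, power, expected rate or effect size, so there is no planned figure to reproduce. All rates below are assumptions.

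**1. Dilution of R/R versus control.** Inputs: T = control coverage by 4/1/2023 (0.40 to 0.60); p = share vaccinated before the first R/R message, equal across arms by randomisation (0.05 to 0.25); r = 1.10, the true risk ratio in those still unvaccinated.

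- Control risk among those still unvaccinated: a = (T − p)/(1 − p).
- Observed risk ratio, all patients: [p + (T − p)r]/T.
- z for control risk c and treated risk t is proportional to √n (t − c)/√[c(1 − c) + t(1 − t)].
- z ratio = z in the unvaccinated subset (with √(1 − p) for its smaller n) divided by z in all patients. Its square is the sample-size equivalent.

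Example, T = 0.50, p = 0.10:
- a = 0.40/0.90 = 0.444, treated 0.489, difference 0.0444.
- All patients: 0.50 versus 0.10 + 0.40 × 1.10 = 0.54, so the risk ratio is 1.080.
- z ratio = (0.0444/√0.4968) × √0.90 ÷ (0.04/√0.4984) = 1.056; squared, 1.115.

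Observed risk ratio, with the squared z ratio in brackets:

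| p | T = 0.40 | T = 0.50 | T = 0.60 |
|---|---|---|---|
| 5% | 1.088 (1.079) | 1.090 (1.051) | 1.092 (1.032) |
| 10% | 1.075 (1.186) | 1.080 (1.115) | 1.083 (1.072) |
| 15% | 1.063 (1.336) | 1.070 (1.198) | 1.075 (1.121) |
| 25% | 1.038 (1.941) | 1.050 (1.465) | 1.058 (1.261) |

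Restricting at the October send is therefore worth between about 3% and about 94% more patients in the same cells.

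**2. The same effect as power.** Now fix q = 0.40, the control risk from October among those unvaccinated, and r = 1.10. Let s be the pre-message share. Use two-sided alpha 0.017 (the SAP does not state sidedness), 1:1 allocation and no clustering. All-dose risks are s + (1 − s)q and s + (1 − s)qr. At s = 0.10 they are 0.460 and 0.496: risk ratio 1.078, difference 3.6 points instead of 4.0. If enough patients are randomised for 80% power in the unvaccinated subset, power with all doses counted is 77%, 74%, 68% and 63% at s = 5%, 10%, 20% and 30%.

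**3. Why the prompt differs.** Suppose the prompt acts only on September doses, with risk ratio 1.10, s = 0.20 and q = 0.40. Without it: 0.20 + 0.80 × 0.40 = 0.520. With it: 0.22 + 0.78 × 0.40 = 0.532. The all-dose risk ratio is 0.532/0.520 = 1.023. Among patients unvaccinated on 1 October it is 0.40/0.40 = 1.000. An October restriction would erase a real effect of the prompt.

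**4. What an earlier baseline filter recovers.** A filter set before the first study message removes only earlier doses. If those are 1%, 2% or 5% of patients, the step 1 formula at T = 0.50 gives about 1%, 2% or 5% in sample-size terms. The larger gains in the table belong to the October restriction alone.

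**The case against.** **Season-long coverage is a legitimate pragmatic estimand.** This stands. Randomisation balances early doses, so the null test is not biased. The number of extra vaccinated patients is also unchanged: at T = 0.50 and p = 25%, 3.3 points among the unvaccinated × 0.75 = 2.5 points overall. The loss is in the relative effect and in power.

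**The Eligibility line may already be an entry gate.** The Protocol says the EHR will identify patients eligible for one or two doses. It does not say whether this decides entry or only dose number and messaging. If it does gate entry, doses between entry and the first October message still count, so the problem shrinks but remains.

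**Stronger readings that do not hold.**
- A reader might infer that doses before any intervention dilute every arm and every risk ratio. The prompt goes out in September, and pre-appointment reminders may reach patients then too, so September doses in those cells can be real effects. For prompt versus fixed portal, the issue is an unequal start of exposure.
- A reader might infer that the two documents score doses before 9/1 in opposite ways. The SAP's "end of flu season vaccination status" is undated and can be shorthand for the Protocol's window. It needs a date, but is not shown to conflict.

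**Conclusion.** The point holds for text and fixed-portal R/R versus control. The outcome window opens before these messages do, and nothing in the entry criteria or the SAP removes or adjusts for patients already vaccinated this season. The direction is clear: the risk ratio moves towards 1 and power falls, with no bias under the null.

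The size cannot be known from the documents. It rests on the assumed 1.10 effect, 40-60% control coverage and 5-25% pre-message share; at 50% coverage, restricting at the October send is worth about 11% more patients for a 10% share and about 46% for a 25% share. This is a cheap improvement to the analysis, not a flaw that invalidates it.

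**What to change.** 1. **Analysis set.** Define it identically in all seven groups: index patients with no 2022-23 season dose dated before one fixed date, at or before randomisation or the first study message. Count doses from that date to 4/1/2023. State the randomisation date and whether the Eligibility line gates entry. Keep the all-index analysis from 9/1 as a sensitivity analysis.
2. **Supportive R/R contrast.** Compare the fixed-text and fixed-portal cells without pre-appointment reminders with control, among patients unvaccinated, by dose date, on the day of the first October send. No study message has reached these cells by then, so the comparison stays randomised. Do not use this restriction for the prompt or pre-appointment contrasts, where it would condition on a post-randomisation event that they can change.
3. **SAP wording.** Use the same dated outcome window as the Protocol.

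**Cost.** Changes of wording and a filter on data already held. Late-arriving external records need one rule by dose date, applied alike in all groups. The primary estimate would then apply to patients still unvaccinated at the start, a slightly narrower population, and the supportive contrast uses only part of the text and portal arms.

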Study Title: Improving Influenza Vaccination Delivery Across a Health System by the Electronic Health Records Patient Portal RCT 5

Initial IRB Approval: 12/20/2017

RCT 5 IRB Approval: 8/18/2022

Clinical Trials Registration: NCT05525494

Statistical Analysis

Primary Analysis

We hypothesize that patients receiving text R/R messages will have higher influenza vaccination rates than portal R/R messages and no R/R; we hypothesize patients receiving the pre-commitment prompt will have higher influenza vaccination rates than standard portal R/R messages and no R/R; and we hypothesize that patients receiving pre-commitment prompts will have higher influenza vaccination rates than no prompts. Primary outcomes (patient receipt of flu vaccine) are binary; our main explanatory variable will be an indicator for the receipt of any portal-based R/R or prompt.

The primary outcome will be the patient's end of flu season vaccination status. Intervention effects will be assessed using mixed effects log-binomial models. Models will contain terms for messaging modality (text v. portal v. none), pre-appointment reminders (sent v. not sent), and, for the portal intervention arm, a pre-commitment prompt (sent v. not sent; this is not included in the text-based arm). Models will adjust for patient characteristics, including age, sex, race/ethnicity, primary language, primary insurer, and prior year vaccination status. Practice random effects will be used to account for clustering of patients by primary care practice. Primary assessment will involve performing model contrasts, and a significance level of 0.017 will be used (3-fold Bonferroni correction of 0.05). To evaluate the combined effect of interventions, we will fit a second model introducing interactions between messaging modality and the other two intervention terms. These analyses will use a significance level of 0.05. Intervention effects will be summarized in terms of risk ratios and 95% confidence intervals.

For RCT #5, individual patients who opt out of text messages will be excluded from the final analysis. In addition, if practices do not send pre-appointment reminders via text, for the pre-appointment analysis the patients from the practice will be excluded from the final analysis. In addition, non-portal users will be excluded from the final analyses.

Secondary Analysis

Secondary analyses will include evaluation of effect modification by patient characteristics. Effect heterogeneity will be evaluated by introducing interaction terms into the primary model specification. All secondary analyses will use a significance level of 0.05. All analyses will be performed using SAS v. 9.4 (SAS Institute Inc., Cary, NC).

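### Testing every primary contrast at a fixed 0.017 is valid, but Holm's step-down procedure is at least as powerful under the same 5% family-wise cap and costs one sentence.

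*SAP*

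**What the plan says.** The second paragraph of the SAP's Primary Analysis states: "Primary assessment will involve performing model contrasts". It then sets one level for all of them: "a significance level of 0.017 will be used (3-fold Bonferroni correction of 0.05". No step-down, ordering or gatekeeping rule appears in either document.

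The three contrasts are not listed. The first paragraph of the same section predicts that "patients receiving text R/R messages will have higher influenza vaccination rates than portal R/R messages and no R/R", and that "patients receiving the pre-commitment prompt will have higher influenza vaccination rates than standard portal R/R messages and no R/R". A third hypothesis compares pre-commitment prompts with no prompts. As worded, that makes up to five comparisons.

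On estimation the SAP says: "Intervention effects will be summarized in terms of risk ratios and 95% confidence intervals". It does not say whether the tests are one- or two-sided. Neither document gives a sample size, expected rates, an effect size, a power target or an allocation ratio.

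**The concern.** A fixed 0.017 holds each contrast to the same bar whatever the others show. Suppose two contrasts have clearly succeeded and the third has p = 0.03. The plan calls the third non-significant. Holm would reject it, and the chance of any false rejection in the family would still be capped at 5%.

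The SAP predicts benefit on several comparisons at once, and that is the setting in which a step-down rule helps most. At stake is power for the second and third findings. The validity of the primary tests is not in question.

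**Working it through.** **Inputs.** From the SAP: overall level 0.05, three tests, one fixed level of 0.017. Assumed, because the documents are silent: two-sided tests, and the power values and allocations named below.

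**1. The plan's figure.** 0.05/3 = 0.01667, printed as 0.017. Three tests at 0.017 sum to 3 × 0.017 = 0.051, so the excess is rounding only.

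**2. Holm never does worse than 0.05/3.** Order the p-values and compare them with 0.05/3, 0.05/2 and 0.05, stopping at the first failure. If a contrast has p ≤ 0.05/3, every smaller p-value is also ≤ 0.05/3 and so passes its own threshold. Holm therefore reaches that contrast and rejects it. The one exception comes from rounding: a smallest p-value between 0.01667 and 0.017 passes the plan's printed level and fails Holm.

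**3. Holm holds 5% under any dependence.** With k true nulls among m contrasts, the first false rejection comes no later than step m − k + 1, where the threshold is 0.05/k. The union bound gives at most k × 0.05/k = 0.05.

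**4. How far a later threshold can help.** The two-sided critical values are z = 2.394 at 0.05/3, 2.241 at 0.025 and 1.960 at 0.05. Power of 80% at 0.05/3 needs a non-centrality of 2.394 + 0.842 = 3.236. Power is then Φ(3.236 − 2.241) = 0.840 at 0.025 and Φ(3.236 − 1.960) = 0.899 at 0.05.

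**5. Simulated power, three independent contrasts, all effects real** (power set at 0.017):

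| Per contrast, fixed 0.017 | Per contrast, Holm | All three, fixed | All three, Holm |
|---|---|---|---|
| 50% | 58% | 12% | 27% |
| 80% | 88% | 51% | 71% |
| 90% | 95% | 73% | 87% |
| 99% | 99.7% | 97% | 99% |

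Power to show at least one effect does not improve (99.2% under both rules in the 80% row). At 80%, with only two effects real, per-contrast power goes from 80% to 83%. With one real it stays at 80%.

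**6. The same with correlated contrasts.** Take text v. portal, text v. none and prompt v. standard portal from the SAP's main-effects model, assuming 1:1:1 arms, 50:50 nested splits and constant variance. The correlations are 0.37, 0.58 and 0.00. With power set at 0.05/3 and all three effects real, the per-contrast gain is about 7-8 points at 50%, 6-8 at 80% (0.80 to 0.86-0.88), 4-5 at 90% and under 1 at 99%. In the 80% case, power for all three rises from 0.58 to 0.75. In 400,000 simulated trials Holm never missed a contrast that Bonferroni at 0.05/3 rejected.

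**7. Gain against sample size.** Assume rates of 45%, 47% and 49% (none, portal, text), equal arms, no clustering and the three pairwise comparisons. Power for portal v. none goes from 35% to 45% at 5,000 per arm, 67% to 80% at 10,000 and 95% to 98% at 20,000. At 500 per arm it goes only from about 4% to 5%.

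**8. Actual family-wise error, three independent contrasts:**

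| Truth | Fixed 0.017 | Holm |
|---|---|---|
| All three null | 0.050 | 0.049 |
| One large effect, two null | 0.034 | 0.049 |
| Two large effects, one null | 0.017 | 0.050 |

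**9. Which contrast gains most.** In the model of step 6, the relative standard errors of text v. portal, text v. none and prompt v. standard portal are 1.73, 1.58 and 2.00. With seven equal cells they are 1.00, 1.29 and 1.00. The prompt contrast is the least precise in the first case and tied for the most precise in the second.

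**The case against.** Bonferroni is a recognised, prespecified and valid choice, and the same remark could be made of any plan that uses it. That stands, and it is why this is an improvement and not an error.

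No loss has been shown in this trial. That also stands. The Protocol draws on portal users across 67 primary care practices, so the sample could be large enough to make the gain negligible. The equal-80% case with 1:1:1 arms is also strained. Multiplying 3.236 by the standard errors gives effects of 5.60 (text v. unprompted portal), 5.12 (text v. none) and 6.47 (prompt). Unprompted portal reminders would then do slightly worse than no reminder. The seven-equal-cell layout avoids that and gives nearly the same gains, but the figures remain illustrations.

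A reader might infer that the plan's stricter level buys nothing. The tables do not support that: when some effects are real, the plan's actual error on the remaining nulls is lower than Holm's. Bonferroni also caps the expected number of false rejections at 0.05, which Holm does not. What is equal is the 5% family-wise cap, which is the standard that the SAP's own correction invokes.

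A reader might also infer that the prompt contrast suffers most because it uses only portal-arm patients. That depends on the allocation and the effects, and the documents state neither.

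Finally, Holm over three p-values protects 5% only if the family really has three members. The hypotheses name up to five comparisons, and the Protocol's Main Outcomes and Measures adds a pediatric primary measure. At 0.017 the levels sum to 5 × 0.017 = 0.085 for five tests and 6 × 0.017 = 0.102 for three contrasts on two measures. This objection stands in full: defining the family comes first and matters more than Holm v. Bonferroni. It does not remove the point, because Holm dominates Bonferroni for any family size.

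**Conclusion.** The point holds as one of efficiency. Apart from the rounding noted above, Holm is uniformly at least as powerful as the planned rule, with no added assumption about how the contrasts are correlated.

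Its size here is unknown. Over the assumptions tried, the per-contrast gain runs from nothing (one real effect) through about 3 points (two real effects at 80% power) to about 6-8 points (three real effects at 80%), and falls below 1 point at 99% power. Individual contrasts can gain more in particular settings: the 67% to 80% rise at 10,000 per arm rests wholly on assumed rates. The documents do not support a claim that this trial loses any stated amount of power, or that its primary tests are invalid.

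**What to change.** Before outcome data are examined:

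1. List the primary contrasts that form the family and state their number m (three, according to the stated correction). Say whether the pediatric primary measure belongs to the family.
2. Replace the sentence that sets the fixed level with: *The m primary contrasts will be tested with Holm's step-down procedure at family-wise 0.05 (0.05/3, 0.05/2, 0.05 for m = 3), with Holm-adjusted p-values reported.*
3. State whether the tests are one- or two-sided, and how the intervals relate to them.

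The cost is a short SAP edit and one option in PROC MULTTEST, within the SAS software already planned. No new data or model is needed. Because Holm has no simple matching simultaneous intervals, the planned 95% intervals would stay unadjusted, or Bonferroni intervals (1 − 0.05/3 = 98.3% for three contrasts) would be used. Little is given up, since the planned 95% intervals already do not match a test at 0.017.
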